## 1 DEFINITIONS AND ABBREVIATIONS

Term	Description
ABG	Air Bone Gap
CBAS	Cochlear Bone Anchored Solutions AB
CHL	Conductive Hearing Loss
COM	Chronic Otitis Media
COMOT	Chronic Otitis Media Outcome Test
CRF	Case Report Form
CRO	Contract Research Organisation
CSOM	Chronic Suppurative Otitis Media
DCF	Data Clarification Form
EC	Ethics Committee
eCRF	Electronic Case Report Form
EDC	Electronic Data Capture
ENT	Ear, nose and throat
GCP	Good Clinical Practices
GNP	Gross National Product
HL	Hearing Level
HRQoL	Health-Related Quality of Life
HUI	Health Utilities Index
ICD-10	International Statistical Classification of Diseases and Related Health Problems – Tenth Revision
ICF	Informed Consent Form
MERI	Middle Ear Risk Index
MHL	Mixed Hearing Loss
OM	Otitis Media
PI	Principal Investigator
PORP	Partial Ossicular Replacement Prosthesis
QoL	Quality of Life
SAP	Statistical Analysis Plan
SSQ	Speech, Spatial and Qualities of Hearing Scale
TORP	Total Ossicular Replacement Prosthesis

## 2 CLINICAL INVESTIGATION SYNOPSIS

Investigation title	A retrospective mapping of health care utilisation and current quality of life status in adult subjects with a history of chronic otitis media with or without cholesteatoma who have undergone a primary tympanoplasty
Short title	MapCOM
Investigation number	CBAS5780
Name of investigational medical device(s)	Not applicable
Intended use of investigational medical device(s)	Not applicable
Name and description of comparator device/product(s)	Not applicable
Estimated recruitment period	Q1 2022 – Q1 2023
Expected duration per subject	The time it takes for the subject to receive, complete and return the informed consent form and the questionnaires and survey. Time for completing the questionnaires is estimated to be 30-40 minutes.
Number of subjects planned	200 subjects
Number of investigational sites planned	6-9 sites
Inclusion criteria	

1. Adult subjects, 18 years or older.

2. Subjects with conductive or mixed hearing loss.

3. Subjects with historically documented diagnosis of Chronic Otitis Media (COM) with or without cholesteatoma in the operated ear.

4. Subjects who have undergone primary tympanoplasty type I-V to improve hearing between 2010-2016.

5. Subjects with a PTA4 air-bone gap <math>\geq 30</math> dB OR PTA4 air-bone gap between 25-30 dB with an air conduction threshold PTA4 <math>\geq 40</math> dB HL within 12 months after primary tympanoplasty in the operated ear.

6. Subjects who have been recommended by their health care professional to try a hearing aid to improve hearing in the operated ear.

7. Pre-op audiogram, maximum 1 year prior to the primary tympanoplasty, and post-op audiogram for the primary tympanoplasty are available.

8. Aided audiogram, unaided if no hearing device is used, available between 2018 and the point of enrolment.

9. Subjects are fluent in the language used for study questionnaires: German, French, Spanish.

10. Subjects are willing and able to provide written informed consent.

	11. Medical Record data is available throughout the defined data search period, from primary tympanoplasty to point of enrolment.
Exclusion criteria	
 
1. Subjects are unable or unwilling to comply with the requirements of the study as determined by the investigator.
 
2. Investigator site personnel directly affiliated with this study and/or their immediate families; immediate family is defined as a spouse, parent, child, or sibling.
 
3. Cochlear employees or employees of Contract Research Organizations or contractors engaged by Cochlear for the purposes of this study.
 

Objectives and Endpoints	
Primary Objective	Primary Endpoint
Map health care utilisation.	
Categorical data collected from primary tympanoplasty to time of enrolment:
 
 
- Number and type of contacts with health care providers
 
- Number and type of interventions and/or procedures (medical examinations, surgical procedures, hearing rehabilitation)
 
- Number and type of medications and therapies
 

Secondary Objectives	Secondary Endpoints
Characterise long-term hearing performance.	
Pre- and post-primary tympanoplasty and a third assessment between 2018 and time of enrolment:
 
 
- PTA4 (0.5, 1, 2 and 4 kHz) for both air and bone conduction, under unaided and when applicable aided conditions.
 

Estimation of health care costs.	
From primary tympanoplasty to time of enrolment:
 
 
- Unit cost
 

Collect socio-economic data, demographics and information on service utilisation.	
At time of enrolment:
 
 
- Client Service Receipt Inventory (CSRI).
 

Assess patient reported outcomes.	
At time of enrolment:
 
 
- Health Utilities Index Mark III (HUI3)
 
- Chronic Otitis Media Outcome Test-15 (COMOT-15)
 
- Speech, Spatial and Qualities of Hearing Scale (SSQ-12)
 

Validate the COMOT-15 in French and Spanish.	Responses from a minimum of 30 subjects per language and audiograms collected within one year of questionnaire completeness.

Exploratory Objectives	Exploratory Endpoints
Develop scoring system to classify severity of middle ear status and relate to surgical outcome.	Middle Ear Risk Index factors (preoperative status, intraoperative findings) and surgical outcomes, if available.
Estimation of productivity losses.	Data on employment status collected in the CSRI survey used to determine the number of lost working hours as a result of COM.

### 3 SCHEDULE OF EVENTS

	Stage 1	Stage 2	Stage 3	Stage 4
Screening	Screening Medical Records for eligibility criteria			
Data collection		Informed consent	Questionnaires and survey (HUI3, COMOT-15, SSQ-12, CSRI).	Information from Medical Records (for complete list see Appendix 1)
Where	At clinic	At subject's home or at clinic if a routine appointment is taking place during study period.	At subject's home or at clinic if a routine appointment is taking place during study period.	At clinic
Timing of data collection	NA	NA	After signed informed consent	After signed informed consent
Performed by	Site personnel	Investigator + Subject	Subject	Site personnel

### 4 BACKGROUND INFORMATION AND RATIONALE

#### 4.1 Introduction

Otitis media (OM) is an umbrella term used to describe inflammatory diseases of the middle ear, including acute OM, which may develop into chronic OM (COM) (1). COM subtypes are categorized as H65-H67 under International Statistical Classification of Diseases and Related Health Problems – Tenth Revision (ICD-10). COM is associated with the development of cholesteatomas (2), which are benign slow-growing tumours that develop in the middle ear space. Middle ear cholesteatomas are categorized under ICD-10 code H71 and are linked to poor patient outcomes since they can erode the middle ear space and middle ear ossicles (3). Global prevalence data show that 65–330 million individuals suffer from COM and that 60% of these individuals have significant hearing impairment (4). COM is characterized by recurring inflammation of the middle ear and mastoid cavity and may clinically present as otorrhea due to tympanic perforation in cases of chronic suppurative otitis media (CSOM) (5). The disease is normally triggered by an acute infection of the middle ear during

childhood (6). The World Health Organization defines OM to be chronic following two weeks of otitis media, whereas other clinical guidelines generally consider that acute OM be classified as COM when patients with tympanic perforations continue to discharge mucoid material for a time period of greater than six weeks to three months, despite medical intervention (7). Recurrent COM can occur due to a combination of several factors and is a significant health burden that affects patient quality of life (QoL) (8). COM is one of the most prevalent global chronic infectious diseases and may lead to hearing impairment (9), including both conductive hearing loss (CHL) and mixed hearing loss (MHL). One of the major causes of COM-associated hearing loss is ossicular discontinuity (10). Hearing losses may range from 20 to 60 dB hearing level (HL) and may be irreversible (11, 12). In children, the resulting hearing loss can negatively impact their speech development, their ability to learn and their behaviour (13, 14). COM in adults has been linked to significantly lower levels of QoL and is associated with anxiety and depression (15). Furthermore, if unsuccessfully treated, several life-threatening complications may arise, including brain abscesses and meningitis (16).

#### 4.1.1 Treatment interventions

COM is a multifactorial disease that is difficult to treat as it can be caused by various mechanisms and co-infections with more than one type of bacteria and/or virus (17). COM treatments principally aim to eradicate infection and restore a healthy middle ear cavity. Current treatment methods include a combination of earwax removal and topical and systemic antimicrobials to eliminate the infection. Surgical interventions include mastoidectomy and reconstruction of the tympanic membrane (18) in order to remove infected tissue and improve hearing (4). Cholesteatomas and ossicular discontinuities typically require a combination of more invasive and complex surgeries that aim to remove tissue overgrowth or to repair and reconstruct the damaged middle ear ossicles through ossiculoplasty. The total ossicular replacement prosthesis (TORP) and partial ossicular replacement prosthesis (PORP) are the two most common types of ossicular chain reconstruction surgeries. However, each surgery is associated with complications and risk of permanent hearing damage (19). Surgical results are also poorly reported and there is a large variation in surgical descriptions and outcomes described in the literature (20). Additionally, clinics in developing countries may not have access to the most modern surgical methods.

#### 4.1.2 Hearing outcomes

Studies use several assessment methodologies and the overall clinical benefits of individual treatments in restoring hearing have not been systematically assessed, particularly not over the long-term. It is frequently reported that surgeries result in non-discharging ears, but it is also obvious that there is a subset of patients who do not show satisfactory improvements in hearing performance following surgery and that post-operative hearing outcomes in some patients actually deteriorate (21, 22). The condition of the ossicular chain is of key importance to hearing outcomes. A retrospective study of 213 patients demonstrated that an intact ossicular chain is significantly associated with improved long-term hearing outcomes after tympanoplasty for perforated COM (23). Patients with a compromised ossicular chain are likely to benefit from bone conduction hearing aids following mastoidectomy (24). It is crucial to understand how surgical intervention could affect hearing since there is extensive evidence of mild to moderate CHL in COM patients before surgery (25). These patients are also predisposed to developing MHL as the disease progresses (26). Studies also stress the need for performing audiology to assess the patients' type and degree of hearing loss prior to treatment intervention since this is not routinely completed (27). Finally, even when audiology is performed the methodology varies, making an accurate comparison difficult.

## 4.2 Findings of Previous Nonclinical and Clinical Studies

### 4.2.1 Nonclinical Data

No relevant non-clinical data is available.

### 4.2.2 Clinical Data

A systematic review investigating long-term hearing outcomes in COM patients treated under the current standard of care has been undertaken (28). The systematic review assessed literature published between 2008-2018 in order to assess the clinical success rate of COM treatments in restoring hearing loss (based on an air-bone gap (ABG) closure within 20 dB) at a minimum follow up time of 12-months in both adult and paediatric patients. Key outcomes from the systematic literature review indicated that 30.0% of patients have a post-operative air bone gap of  $\geq 20$  dB. Data also show that 14.7% of patients have post-operative complications, including 7.0% of patients in which a perforation of the tympanic membrane persisted at long-term follow up.

## 4.3 Study Rationale

The rational for conducting this primarily descriptive study is to broaden the understanding of the treatment pathways and health care interventions that follow a primary tympanoplasty (middle ear reconstructive surgery) among patients with COM, with or without cholesteatoma. An improved understanding of the treatment pattern will guide clinicians in making well-informed treatment decisions in order to improve the hearing and QoL of patients and more efficiently utilise available health care resources.

## 5 MEDICAL DEVICE INFORMATION

### 5.1 Identity and Description of the Investigational Medical Device (IMD)

Not Applicable.

### 5.2 Identity and Description of the Comparator

Not Applicable.

### 5.3 Accessory Device Requirements

Not Applicable.

## 6 OBJECTIVES

### 6.1 Primary Objective

1. Map health care utilisation.

### 6.2 Secondary Objectives

1. Characterise long-term hearing performance.
2. Collect socio-economic data, demographics and information on service utilisation.
3. Estimation of health care costs.

4. Assess patient reported outcomes.
5. Validate the COMOT-15 in French and Spanish

[figure not shown]
## 6.3 Exploratory Objectives

1. Develop scoring system to classify severity of middle ear status and relate to surgical outcome.
2. Estimation of productivity losses.

# 7 DESIGN OF THE CLINICAL INVESTIGATION

## 7.1 General

This is *primarily a retrospective study* to evaluate the standard of care of patients with COM across three countries in Europe. The study is therefore set up as a multicentre clinical investigation with a retrospective part (medical record review) and a minor prospective element with questionnaires and a survey completed by the subjects.

**Figure 1:** Schematic illustration of the clinical investigation elements

The subjects shall include men and women aged 18 years or older who underwent primary tympanoplasty to improve hearing between 2010-2016 and have a historically documented diagnosis of COM, with or without cholesteatoma in the operated ear. Subjects will be screened and 200 subjects will be enrolled in the clinical investigation across the 6-9 investigation sites in Germany, Spain and France. The study will aim to enrol subjects with an even distribution across all study sites. If any site has difficulties with recruitment the remaining sites can recruit more subjects, so the total recruitment is not affected, upon agreement with the Sponsor. In view of a possible situation where last recruitment efforts may result in exceeding the needed 200 subjects, no more than 10% over recruitment is expected.

In case no other follow-up visit to the clinic is planned within the study recruitment period subjects who have had an audiogram done between 2018 and the point of enrolment will be sent the ICF, questionnaires and survey via registered mail for completion at home. Subjects who are planned to have a follow-up audiogram collected within the study recruitment period will be asked to complete the ICF, questionnaires and survey at the time of their appointment. The medical record search for data extraction will be done at the clinic. See section 3. *Schedule of Events*.

The primary endpoint is to collect categorical data; number and type of contacts with health care providers, number and type of interventions and/or procedures and number and type of medications and therapies to map health care utilisation. Health care utilisation data will be analysed in patient years, from primary tympanoplasty to point of enrolment. Secondary endpoints are PTA4 to give information about hearing performance, unit cost for an estimation of health care costs, CSRI survey to collect socio-economic data, demographics and information on service utilisation, questionnaires (HUI3, COMOT-15, SSQ-12) to assess current patient reported outcome and responses from a minimum of 30 subjects per language (29) and audiograms collected within one year of questionnaire completeness to validate COMOT-15 in French and Spanish. Exploratory endpoints are data on employment status for an estimation of productivity losses and Middle Ear Risk Index factors and surgical outcome to develop a scoring system to classify severity of middle ear status and relate to surgical outcome, if needed information is available.

### 7.1.1 Design Rationale

This study is designed to collect information regarding health care interventions that follow a primary tympanoplasty with residual hearing loss among adult subjects with diagnosis of COM, with or without cholesteatoma. A multicentre set-up is necessary to accurately capture the standard of care as this can vary at each site, as determined by treatment practice surveys at potential sites and it is important that we capture outcomes on all potential interventions that may be offered as part of standard care. The rationale to collect information from subjects who underwent a primary tympanoplasty procedure between 2010-2016 is to increase the likelihood of availability of electronic medical records data as these systems have only typically been introduced in recent years. This inclusion time frame is also important to capture the current standard of care rather than outcomes from obsolete procedures and to find enough subjects that have at least five years follow-up data so that we may capture patients who have reached a steady state. Subjects with single-sided deafness are not eligible for the study as COM with or without cholesteatoma leads to mainly conductive or mixed hearing loss. Paediatric subjects are excluded from the study as tympanoplasties are delayed until adulthood in some clinics.

## 7.2 Subjects

Written informed consent must be obtained from the subject or its legally authorised representative before any data is collected.

Eligibility of subjects must be supported by the inclusion and exclusion criteria listed below.

### 7.2.1 Inclusion Criteria

Subjects must meet all of the inclusion criteria described below to be eligible for this clinical investigation.

1. Adult subjects, 18 years or older.
2. Subjects with conductive or mixed hearing loss.
3. Subjects with historically documented diagnosis of Chronic Otitis Media (COM) with or without cholesteatoma in the operated ear.
4. Subjects who have undergone primary tympanoplasty type I-V to improve hearing between 2010-2016.
5. Subjects with a PTA4 air-bone gap  $\geq 30$  dB OR PTA4 air-bone gap between 25-30 dB with an air conduction threshold PTA4  $\geq 40$  dB HL within 12 months after primary tympanoplasty in the operated ear.
6. Subjects who have been recommended by their health care professional to try a hearing aid to improve hearing in the operated ear.
7. Pre-op audiogram, maximum 1 year prior to the primary tympanoplasty, and post-op audiogram for the primary tympanoplasty are available.
8. Aided audiogram, unaided if no hearing device is used, available between 2018 and the point of enrolment.
9. Subjects are fluent in the language used for study questionnaires: German, French, Spanish.
10. Subjects are willing and able to provide written informed consent.
11. Medical Record data is available throughout the defined data search period, from primary tympanoplasty to point of enrolment.

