## 9.7 Secondary Endpoint Analyses

### Hearing performance

Audiogram data (see 9.2.2) collected pre- and post- primary tympanoplasty and between 2018 and point of enrolment will be compared to investigate how the standard of care impacts the subjects' hearing, when feasible. Wilcoxon signed rank test will be used to compare the audiometric test results.

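### The third audiogram is placed by calendar date rather than time since surgery, and the pooled hearing comparison does not account for the resulting spread in follow-up

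*Combined protocol and SAP*

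**What the plan says.** The first secondary objective in section 6.2 is "Characterise long-term hearing performance". Section 9.2.2 measures it by PTA4 before surgery, after surgery and at a third assessment.

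The timing rules are in section 7.2.1:
- Criterion 4, surgery: "Subjects who have undergone primary tympanoplasty type I-V to improve hearing between 2010-2016".
- Criterion 5, the post-operative hearing-loss requirement: "within 12 months after primary tympanoplasty in the operated ear".
- Criterion 8, third assessment: an aided audiogram, or an unaided one for subjects without a device, "available between 2018 and the point of enrolment".

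Section 2 estimates recruitment as "Q1 2022 – Q1 2023". Section 7.2.5 recruits backwards in time, beginning with the last 2016 operation. Section 7.3.2.2 and Appendix 1 extract the latest available audiogram. Section 7.1.1 defends the surgery window partly because it should find enough subjects with "at least five years follow-up data so that we may capture patients who have reached a steady state".

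For the analysis, section 9.7 says that the "Wilcoxon signed rank test will be used to compare the audiometric test results", where the comparison is feasible. It mentions no stratification, adjustment or sensitivity analysis for time since surgery. Utilisation and costs, by contrast, are analysed in patient-years (sections 7.1, 9.2.2, 9.6 and 9.7).

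**The concern.** A window fixed by calendar date gives each subject a different follow-up time, depending on the year of surgery and on when the ear was last tested. A paired test on the pooled differences then describes a mixture: for some subjects the change over little more than a year, for others the change over a decade. If hearing drifts with time, the result depends on the mix of intervals that happens to be recruited. The plan itself expects some drift, since section 4.1.2 notes that mixed loss may develop as the disease progresses.

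The comparison most exposed is post-operative against third audiogram, because the gap between those two can be short. Pre-operative against third also mixes follow-up times, but it always spans the operation and at least a year after it. Pre-operative against post-operative is not touched. At stake is whether a reader of the report can tell a one-year result from a ten-year result.

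**Working it through.** **Inputs.** Surgery 1 Jan 2010 to 31 Dec 2016 (criterion 4). Third audiogram 1 Jan 2018 to enrolment (criterion 8). Enrolment at its widest 1 Jan 2022 to 31 Mar 2023 (section 2). Post-operative audiogram up to 12 months after surgery (criterion 5).

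**The plan's own figure.** Shortest time from surgery to enrolment: 31 Dec 2016 to 1 Jan 2022 = 1827 days; 1827 / 365.25 = 5.0 years. The five-year follow-up in section 7.1.1 is therefore reproduced, but for surgery to enrolment.

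**Surgery to third audiogram.**
- Shortest: 31 Dec 2016 to 1 Jan 2018 = 366 days; 366 / 30.4375 = 12.0 months.
- Longest: 1 Jan 2010 to 31 Mar 2023 = 4837 days; 4837 / 365.25 = 13.2 years.

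By year of surgery, the minimum runs from 31 December of that year to 1 Jan 2018, and the maximum from 1 January of that year to 31 Mar 2023:

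| Surgery year | Minimum (years) | Maximum (years) |
|---|---|---|
| 2010 | 7.0 | 13.2 |
| 2011 | 6.0 | 12.2 |
| 2012 | 5.0 | 11.2 |
| 2013 | 4.0 | 10.2 |
| 2014 | 3.0 | 9.2 |
| 2015 | 2.0 | 8.2 |
| 2016 | 1.0 | 7.2 |

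Five years is guaranteed only for operations up to 2012. For one subject the third audiogram date can move by at most 1 Jan 2018 to 31 Mar 2023 = 1915 days = 5.2 years; the rest of the overall range comes from the year of surgery.

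**Post-operative to third audiogram.** For an operation on 31 Dec 2016, a post-operative test on 31 Dec 2017 and a third test on 1 Jan 2018 both qualify, one day apart. This is the limiting case, not a typical one.

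**Share under five years.** The documents do not give the dates, so this is a range under assumptions: surgery and enrolment dates uniform, and the audiogram uniform over the stated period before enrolment (simulation, 400,000 draws).

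| Surgery dates | Audiogram 2018 to enrolment | Last 24 months | Last 12 months |
|---|---|---|---|
| 2016 only | 76% | 44% | 13% |
| 2014-2016 | 54% | 17% | 4% |
| 2010-2016 | 25% | 7% | 2% |

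The 13% can be checked by hand. Let x be years from 1 Jan 2022 to enrolment (0 to 1.25), u years from audiogram to enrolment (0 to 1), and y the position of surgery within 2016 (0 to 1). The interval is 6 + x − u − y, which is below 5 when u + y > 1 + x. For x below 1 that has probability (1 − x)²/2, and otherwise 0. Averaging over x gives (1/1.25) × (1/6) = 0.133. With surgeries spread over the seven years 2010-2016, only the 2016 operations can fall short, so 0.133 / 7 = 0.019, the 2% in the last cell.

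Intervals under two years are much rarer: 10.9%, 3.6% and 1.6% down the first column, and none in the other two.

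**The case against.** The strongest reply is that the plan extracts the latest available audiogram (section 7.3.2.2, Appendix 1). A January 2018 test counts only if the subject had no later one in the four or more years before enrolment. Other text also favours recent tests. Section 7.1 ties questionnaire completion to planned audiogram visits. The COMOT-15 validation (section 7.3.2.1) needs at least 30 French and 30 Spanish subjects with an audiogram within 12 months of the questionnaire; for them the earliest third audiogram is about 1 Jan 2021, and 31 Dec 2016 to that date is 1462 days, or 4.0 years. A reader might infer from the date rules that near-duplicate pairs are likely and shrink the estimated change by some fixed fraction. The documents do not support that: backward recruitment fixes the surgery date, not the audiogram date, and any dilution fraction would be assumed.

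Second, a reader might infer that the plan defines long-term hearing as five years or more and so misses its own objective. It does not. Section 7.1.1 uses five years to justify the surgery window. The only follow-up floor that the documents attach to long-term hearing outcomes is the 12 months of the systematic review in section 4.2.2, which every permitted third audiogram meets.

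Third, the comparison is descriptive and secondary, and section 9.3 states no hypotheses.

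These replies limit the point but do not remove it. The version 4.0 rationale in section 25 says that criterion 8 was changed to admit subjects without an audiogram in the 12 months before enrolment, so older audiograms are expected. Recruitment starts with 2016, the year with the shortest permitted intervals. And nothing in section 9.7 would show a reader what mix of intervals resulted.

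**Conclusion.** The point holds as a minor one. The permitted interval from surgery to third audiogram is 12.0 months to 13.2 years; five years is not assured for operations in 2013-2016; and the pooled signed rank test mixes these follow-up times under an objective of long-term hearing, mainly in the post-operative versus third comparison.

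The range rests on the protocol's dates, with the recruitment quarters taken at their widest. The share under five years is unknown: 2% to 76% is the spread of the scenarios, not an estimate. No size of bias in PTA4 can be derived, because the documents give no rate of hearing change over time. It is not shown that the objective goes unanswered. The primary utilisation endpoint is unaffected.

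**What to change.** Leave eligibility unchanged and keep all subjects. Add to the hearing performance part of section 9.7:

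1. Report the distribution (median, quartiles, range) of time from surgery to third audiogram and from post-operative to third audiogram.
2. Analyse PTA4 and air-bone gap with years since surgery as a covariate, for example a mixed model over the three audiograms with a random subject effect, a pre- versus post-operative term and a slope for years after surgery. The signed rank test can stay as a simple summary.
3. As a sensitivity analysis, show results separately for third audiograms under five years and at five years or more.

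Step 3 should not become a restriction. If 2016 operations dominate, a five-year cut could drop 13% to 76% of subjects under the scenarios above, and it may favour ears still under follow-up.

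The cost is slightly more analysis work, with small numbers in some time bands. No new data are needed: Appendix 1 records the audiogram date, and the tympanoplasty date is already required for eligibility, recruitment order and patient-years. Appendix 1 lists the surgery date in a block marked as collected if available, so the sponsor should confirm that the primary tympanoplasty date is captured for every subject.
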